Research Study Proposal

Title of Study: A Prospective Study to Examine Patient Satisfaction, Function, and Limb Alignment Outcomes for Mako versus Non-Mako Total Knee Replacements

A. Background and Statement of Context

In recent years, orthopedic surgeons have increasingly embraced robotic-assisted surgical techniques to improve the accuracy and precision of total hip and knee arthroplasty, and partial knee arthroplasty. The stages of computer-assisted surgery include preoperative imaging and planning, intraoperative design and execution, and postoperative evaluation [1]. Several prior studies have attempted to validate the clinical efficacy and cost efficiency of robotic assisted total hip replacement [2-6]. However, few studies have addressed the clinical and radiographic outcomes of robotic assisted total knee arthroplasty (TKA), with no consensus in regards to meaningful clinical value [7]. In November 2015, as a pioneer user, Virtua Joint Replacement Institute (JRI) adopted the Mako System (Stryker, Kalamazoo, MI) - a robotic-arm assisted surgery technology based on CT image guided navigation. Today, 5 surgeons have performed a total of 471 TKA cases done to date using the Mako device. This study is aimed at contributing to the nascent body of literature on robotic-assisted TKA (RA-TKA) by comparing the patient reported outcomes and accuracy of implant placement for patients receiving RA-TKA versus TKA with traditional mechanical guides (MG-TKA).

B. Study Questions/Objectives and Hypotheses

Study Objectives

The purpose of this study is to compare the efficacy (patient reported outcomes and radiographic results) for RA-TKA versus MG-TKA. Specifically, when compared to their control group counterparts that undergo MG-TKA, we hypothesize that the intervention group treated with RA-TKA will, following surgery, experience:

1. Higher patient reported Forgotten Joint Score (FJS), 3 months, 6 months, 12 months, 2 years, and 5 years postoperatively (primary outcome measure).

2. Higher patient reported Knee injury and Osteoarthritis Outcome Score (KOOS), 3 months, 6 months, 12 months, 2 years, and 5 years postoperatively.

3. Higher patient reported Veterans Rand 12-item Health Survey Score (VR-12), 3 months, 6 months, 12 months, 2 years, and 5 years postoperatively.

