The primary outcome measure is the difference in mean Forgotten Joint Score (FJS) between the two groups of patients for which the two sample t-test will be utilized. The FJS is a self-completed 12-item questionnaire used to assess patients' awareness of their artificial joint during activities of daily living on an awareness scale of 0 (never) to 4 (mostly). There is a 6th response of "not relevant for me", and this is treated as a missing value and not included in the number of completed items. All the responses are summed up and divided by the number of completed items, and the mean value is then multiplied by 25 to obtain a total score from 0 to 100. This score is then subtracted from 100 to change the direction of the final score in such a way that higher scores indicate a higher degree of forgetting the artificial joint [8]. The FJS (Appendix 1) will be administered to the patients during their regularly scheduled 3, 6, and 12 months, 2 year, and 5 year postoperative office visits.

A second outcome measure is the difference in Knee injury and Osteoarthritis Outcome Score (KOOS) between the two groups of patients for which the two sample t-test will also be utilized. The KOOS is a knee-specific instrument used to evaluate short-term and long-term symptoms and function in subjects with knee injury and osteoarthritis. It consists of 42 questions in 5 subscales; Pain, other Symptoms, Function in daily living (ADL), Function in Sport and Recreation (Sport/Rec), and knee-related Quality of Life (QOL). All questions are assigned a score of 0 (No Problems) to 4 (Extreme Problems). Scores are transformed to a 0 to 100 scale, with zero representing extreme knee problems and 100 representing no knee problems [9]. The KOOS will be administered to the patients during their regularly scheduled 3, 6, and 12 months, 2 year, and 5 year postoperative office visits.

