A third outcome measure is the difference in mean scores for the Veterans RAND 12 Item Health Survey (VR-12) between the two groups for which the two sample t-test will be utilized. The VR-12 is a 12-item questionnaire corresponding to eight principal physical and mental health domains including general health perceptions, physical functioning, role limitations due to physical and emotional problems, bodily pain, energy-fatigue, social functioning and mental health. The 12 items are summarized into two scores: a Physical Component Score (PCS) and a Mental Component Score (MCS) which then provides an important contrast between the respondents' physical and psychological health status [10]. The VR-12 will be administered to the patients during their regularly scheduled 3, 6, and 12 months, 2 year and 5 year postoperative office visits.

The radiographic outcomes will be studied in two ways.

1) The mechanical alignment of the entire post-operative limb will be measured at 6 weeks by long-limb radiograph cassettes and compared to the pre-operative plan for accuracy and deviation less than or greater than 3 degrees from the intended target. From each treatment group, the percentage of patients with radiographic outliers (deviation greater that 3 degrees from the expected implant placement) will be compared. The z-test for proportions will be used for this assessment.

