2) Pre-operative and post-operative CT scans will be performed on all patients and component rotation will be measured and compared to pre-operative target values for each. The rotational femoral component angle is defined as the angle between the surgical epicondylar axis and the posterior condylar line of the femoral component. The rotational tibial component angle is defined as the angle between a line connecting the centre of the tibial component and the medial third of the tibial tubercle and a line perpendicular to the posterior condylar line of the tibial component [14]. A Mann-Whitney U test can determine statistically significant differences (p < 0.05) in absolute value from the target angles between the two treatment groups using these parameters. Fisher's exact probability test will be used to compare the quality of implantation, measured against the ideal position, between the two systems with these parameters (p < 0.05). The correlation between error in rotational alignment and the functional score for both groups can be measured using Spearman's correlation coefficient by rank test (p < 0.05). Preoperative and postoperative posterior femoral condylar offsets will be measured in the sagittal plane for the preoperative femur and the femoral component. The maximum thicknesses of the medial and lateral posterior condyles will be measured from the edge of each condyle to a line tangential to the posterior cortex of the femoral shaft [15].

Two blinded reviewers will assess each patient film to assure intra-observer and inter-observer reliability. The chance-corrected κ -coefficient will be calculated to determine intra- and inter-observer agreement [16].

All statistical analyses will be conducted at the 0.05 level of significance.

Power/Sample Size

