Giesinger et al. [11] reported that for 98 TKA study patients, their 2-month, 6-month, 1-year, and 2-year postoperative FJS mean (standard deviation) were respectively: 20.9 (17.4), 41.7 (25.9), 67.3 (27.2), and 80.8 (25.8). For the purpose of our power analysis therefore, we find it reasonable to assume a 10 point difference in mean FJS between the two patient groups as the effect size to detect and a standard deviation of 27.2. For an 80% power at a 0.05 level of significance, the minimum required sample size for each group is 118. To account for possible crossovers, we apply a 5% markup against the statistically derived sample size to arrive at a minimum of 124 patients needed for each group for a total of 248 patients to be enrolled in the study.

G. Study Duration and Subject Enrollment Feasibility

Between Jan 1, 2017 to November 16, 2017, the Virtua JRI averaged about 128 TKA cases a month. If we assume that 25% of eligible patients can be enrolled into the study, then we estimate to average about 32 study patients per month. For the 248 patients needed in total for the study therefore, we anticipate an 8-month study enrollment completion timeline.

H. Study Limitations

The main limitation we anticipate is with regards to the possibility of patients declining to participate in the study due to concerns of leaving their surgical assignment to chance. By assuming only a 25%

enrollment rate however, combined with the large volume of TKA cases we see at the Virtua JRI, the projected 8-month enrollment completion timeline is very realistic.

I. Stakeholder Communication Plan

The physician assistants (PAs) will play a crucial role in enrolling patients for the study. All the PA's at the Virtua JRI will be trained on the study protocol so that they are well equipped to address patients' questions/concerns. The PAs will also take the lead on administering the patient reported outcomes surveys (FJS, KOOS, VR-12) and they will receive the relevant training to administer these effectively.

J. Dissemination Plan for Study Findings

The Virtua JRI surgeons plan to publish the study outcomes in a reputable peer-reviewed orthopedic journal such as the Journal of Arthroplasty.

K. Itemized Study Budget

Department	Estimated Labor Hours	Estimated Supply Cost (\$)
Virtua Clinical Research Department	80	
– Statistical/IRB/Manuscript support		
Virtua Voorhees Radiology		\$24,800 (Estimated \$100 per post- operative CT scan for 248 study patients)

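### The two-sample t-test, the only between-group method named for FJS, KOOS and VR-12, cannot use a patient's other visits, which costs precision at 2 and 5 years if forms are missing

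*Combined protocol and SAP*

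**What the plan says.** Section B (Study Objectives) states the first hypothesis for five times: "Higher patient reported Forgotten Joint Score (FJS), 3 months, 6 months, 12 months, 2 years, and 5 years postoperatively (primary outcome measure". KOOS and VR-12 carry the same five times. Section F (Statistical Methods) has each instrument completed at the "regularly scheduled 3, 6, and 12 months, 2 year, and 5 year postoperative office visits" and lists no preoperative administration of any of the three.

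The only between-group method named for these scores is the two-sample t-test. For FJS the outcome is the "difference in mean Forgotten Joint Score (FJS) between the two groups of patients for which the two sample t-test will be utilized". KOOS is compared "between the two groups of patients for which the two sample t-test will also be utilized" and VR-12 "between the two groups for which the two sample t-test will be utilized".

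The single missing-data rule concerns FJS items marked as not relevant: "this is treated as a missing value and not included in the number of completed items". Nothing is said about a patient who misses a whole visit. No mixed model, imputation, analysis population or sensitivity analysis is described. The 5% markup in Power/Sample Size is for crossovers, not for loss to follow-up.

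**The concern.** A two-sample t-test takes one value per patient. With five hypothesised times and no rule for a missed visit, a patient with 3-, 6- and 12-month scores but no 2-year form contributes nothing to a 2-year comparison, although those earlier scores are informative about the missing one. The hypotheses run to 5 years and the forms are completed at office visits, so some missing late scores should be expected.

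Two things are at stake. The first is precision, which is lost even when patients go missing at random. The second is possible bias in the arm difference if those who stop attending differ in their earlier scores. A repeated-measures model uses the earlier scores and so addresses both, as far as loss is explained by what was recorded.

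**Working it through.** **1. The plan's own figure.** Inputs from Section F: difference 10, SD 27.2, 80% power, alpha 0.05. The document states: "For an 80% power at a 0.05 level of significance, the minimum required sample size for each group is 118". The normal formula, two-sided, gives n = 2(1.960 + 0.842)² × 27.2² / 10² = 116.1, so 117. The noncentral-t version gives 117.1, so 118, which matches. The markup gives 118 × 1.05 = 123.9, so 124. The sample-size arithmetic is sound.

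**2. How much slack there is.** Normal-approximation power with m scored patients per arm is Φ(10 / (27.2√(2/m)) − 1.96).
- m = 124: Φ(2.895 − 1.96) = 82.5%.
- About 7% missing (m about 115): just under 80%.
- 30% missing (m = 86.8): Φ(2.422 − 1.96) = 67.8%.

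If earlier scores explain a share R² of the variance and a fraction d is missing at random, with the earlier scores present, the effective number is m/(1 − R²d). At d = 0.30 this is 86.8/0.925 = 93.8 for R² = 0.25 (power 71.2%) and 86.8/0.808 = 107.4 for R² = 0.64 (power 76.9%). Part of the lost power comes back, not all of it.

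**3. Precision by visit.** The documents give no missing rate and no between-visit correlation, so both are assumed: cumulative missing 3/6/12/22/35% at the five visits (share observed q = 0.97, 0.94, 0.88, 0.78, 0.65), monotone and random; equal correlation r of 0.5 or 0.7 between any two visits. The variance explained by j earlier visits is R²ⱼ = j r² / (1 + (j − 1)r):
- r = 0.5: 0.250, 0.333, 0.375, 0.400
- r = 0.7: 0.490, 0.576, 0.613, 0.632

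The proportional fall in variance at visit k is Σⱼ (R²ⱼ − R²ⱼ₋₁)(1 − qₖ/qⱼ), summed over the earlier visits. For 5 years with r = 0.5: 0.250 × 0.330 + 0.083 × 0.309 + 0.042 × 0.261 + 0.025 × 0.167 = 0.123.

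| Visit | Formula, r = 0.5 | Formula, r = 0.7 | Simulated range |
|---|---|---|---|
| 3 months | 0 | 0 | – |
| 12 months | 2.9% | 5.1% | 2–5% |
| 2 years | 6.8% | 11.5% | 8–15% |
| 5 years | 12.3% | 20.1% | 12–19% |

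The simulated range comes from simulated trials under the same assumptions. The formula suggests that its top value at 2 years is partly simulation noise.

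**4. Bias of the complete-case difference.** Simulated trials, 124 per arm. Set-up A uses the SDs that Section F cites (the 2-month value standing for 3 months, the 2-year value for 5 years) and the missing rates above. Set-up B uses SD 27.2 throughout, with a nominal 15% lost by 2 years and 30% by 5 years. Where loss depends on scores, the log-odds of dropping out rise by 0.7 per SD of lower previous score.

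| Loss mechanism | 2 years | 5 years |
|---|---|---|
| Unrelated to scores | about 0 | about 0 |
| Equal in both arms, no true effect | about 0 | about 0 |
| Equal in both arms, true effect 10 | −0.3 to −0.6 | −0.6 to −1.1 |
| Control arm only, true effect 10 | −1.7 to −2.9 | −3.3 to −4.9 |

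The repeated-measures estimate stayed within about 0.3 points of the truth throughout, as it should when loss depends only on recorded scores. For scale, with 35% missing the standard error of the difference is 25.8√(2/80.6) = 4.1 points (4.3 with SD 27.2), so 1.1 points is about a quarter of a standard error.

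**The case against.** **The plan does not say that a t-test will be run at each visit.** Correct. That is an inference from five hypothesised times, one named method and no named primary visit. The SD of 27.2 equals the cited cohort's 1-year value, so 12 months may be the intended comparison. The gain there is small: 2–5% of variance is about 1–2.5% of the standard error.

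**A reader might infer that the t-test is unbiased only if the missing patients are a random subset of each arm.** That holds for each arm mean, not for the difference. When loss depends on scores in the same way in both arms and there is no true effect, the bias cancels; with a 10-point effect it is a modest attenuation. Equal-mechanism loss creates no spurious benefit.

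**A reader might also infer that the 2- and 5-year results will be off by a material share of the 10-point target.** This needs loss that depends on scores differently by arm. Nothing in the documents suggests it. Section E blinds patients with sham stab incisions and keeps postoperative care the same in both groups, which makes it less expected.

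**The bias figures assume unbounded normal scores, whereas FJS stops at 100.** With mean 80.8 and SD 25.8, about 23% of simulated control scores exceed 100, since (100 − 80.8)/25.8 = 0.74. Clipping to 0–100 reduces the one-arm bias to about −1.5 to −2.1 at 2 years and −2.5 to −3.5 at 5 years, but the true difference also shrinks to about 7. The direction survives; the exact sizes should not be leaned on.

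**With complete data the two methods agree, and the t-test matches the sample-size calculation.** True, and a reason to treat this as an improvement rather than an error. What stands is the precision argument, which needs no bias scenario.

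**Conclusion.** The point holds as a case for a better method, not as a finding that the t-test is invalid. The documents support three statements: scores are collected and hypothesised at five times, only a two-sample t-test is named, and no rule covers a missed visit. That test cannot draw on a patient's other visits.

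The firm consequence is lost precision that grows with follow-up: nothing at 3 months, little at 12 months, roughly a tenth of the variance at 2 years and an eighth to a fifth at 5 years. This rests on the assumed missing rates and correlations, and the loss is smaller if fewer forms are missing or visits correlate less.

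Bias is a possibility whose size depends on an unknown mechanism. It ranges from about zero, through about a point or less when loss depends on scores equally in both arms, to several points in an arm-specific worst case. The documents do not settle which applies, or in which direction.

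**What to change.** For FJS, each KOOS subscale, and VR-12 PCS and MCS, make the main analysis one likelihood-based mixed model for repeated measures:
- all randomised patients with at least one score;
- arm, visit and arm-by-visit as fixed effects;
- unstructured covariance, REML, Kenward-Roger degrees of freedom;
- arm difference and 95% CI reported at each visit.

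Keep the two-sample t-test as a supporting analysis. Add a sensitivity analysis, for example delta-adjusted, for loss that depends on scores that were never recorded, because the mixed model does not protect against that. The model gives the contrast at whichever visit is named primary; naming that visit and allowing for loss to follow-up in the sample size are separate matters.

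The cost is a paragraph of analysis-plan wording, written before outcome data are analysed, and slightly more analysis work. No new data are needed. The model assumes that missingness is explained by the recorded scores, and that assumption should be stated.

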4. Fewer radiographic outliers (deviation greater that 3 degrees from planned mechanical limb alignment). The radiographic analysis will be performed postoperatively using long limb plain radiographs.

C. Study's Alignment with Virtua's Mission, Vision, Values and Strategic Imperatives

Though the Virtua JRI remains at the forefront of RA-TKA, through this study Virtua Health may become the first health system to report better clinical outcomes of TKA utilizing RA-TKA versus the standard MG-TKA. Moreover, these data may help demonstrate greater value achieved by the application of RA-TKA in TKA practiced at Virtua, and provide an evidence-base of higher quality and value to insurers and population-based health providers.

D. Study Design

Type of Study Design

This is a randomized, controlled, prospective, single-blind study.

Study Inclusion Criteria

Patients who meet all of the following inclusion criteria may be eligible to participate in the study:

1. Age 18 or older

- 2. Diagnosed with primary osteoarthritis and cleared to undergo total knee arthroplasty at the Virtua JRI
- 3. Willing to provide informed consent, participate in study, and comply with study protocol

Study Exclusion Criteria

Patients who meet any of the following criteria may not be eligible to participate:

1. Pregnant or contemplating pregnancy prior to surgery;

2. Worker's compensation or personal injury related to knee (clinical outcomes have been shown to be less predictable and often poorer in this patient group; there may also exist potential issues with reimbursement)

3. Post-traumatic arthropathy (clinical outcomes have been shown to be less predictable; pre-operative deformity and risk factors are greater and difficult to propensity-match between groups)

 Self-pay patients or patients whose insurance are known to typically decline reimbursement for preoperative CT scans

E. Study Procedures

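### Limb alignment is measured in degrees but tested only as a percentage beyond 3 degrees; a supporting analysis of mean absolute deviation would be a cheap addition, with a power effect that depends on the shape of the errors

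*Combined protocol and SAP*

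**What the plan says.** Hypothesis 4 in section B (Study Objectives) is that the robotic group will have fewer limbs more than 3 degrees from the planned mechanical alignment.

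Section F, Statistical Methods, radiographic outcome 1, describes the measurement: "The mechanical alignment of the entire post-operative limb will be measured at 6 weeks by long-limb radiograph cassettes". The result is set against the pre-operative plan, both for accuracy and for falling inside or outside 3 degrees. One comparison follows: "the percentage of patients with radiographic outliers (deviation greater that 3 degrees from the expected implant placement) will be compared". One test is named: "The z-test for proportions will be used for this assessment". No test is attached to the word accuracy.

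Radiographic outcome 2, component rotation on CT, is handled differently: "A Mann-Whitney U test can determine statistically significant differences (p < 0.05) in absolute value from the target angles between the two treatment groups". Fisher's exact test is added there for quality of implantation.

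The significance level is general: "All statistical analyses will be conducted at the 0.05 level of significance". Section F, Power/Sample Size, sizes the trial on the Forgotten Joint Score (FJS) alone. No power is given for any radiographic outcome.

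**The concern.** Reducing an angle to a yes/no at 3 degrees treats 0.2 and 2.8 degrees as the same result, and 3.1 and 8 degrees as the same result. If the robotic technique tightens alignment across the board, much of that signal lies below the cut-off, where a test of proportions cannot see it. A real gain in accuracy could then be reported as no difference, although the data to show it had been collected. A mean difference in degrees with a confidence interval would also tell the reader something that a difference in percentages at one cut-off does not.

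The plan already accepts absolute deviation as an analysis variable for rotation. Limb alignment, which is in the study title and has its own numbered hypothesis, has no such analysis.

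**Working it through.** **The plan's own figure.** With an FJS difference of 10, SD 27.2, two-sided 0.05 and 80% power, n = 2 × (1.960 + 0.842)² × (27.2/10)² = 116.1, so 117 by the normal formula. The t-based solution is 117.1, rounded up to the stated 118. Then 118 × 1.05 = 123.9, so 124 per group and 248 in total. The stated size reproduces; 124 per group is used below.

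**Inputs.** From the documents: the 3-degree cut-off, the z-test, the 0.05 level and 124 per arm. Everything about the errors (SD, centre, shape) is assumed, because the documents give none of it.

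**One case by formula: normal errors centred on the plan, SD 2.0 v 1.5 degrees.**

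- Outlier rate = 2 × [1 − Φ(3/SD)]. 3/2.0 = 1.5 gives 13.4%; 3/1.5 = 2.0 gives 4.6%.
- z-test: difference 0.0881; pooled rate 0.0896; null SE = √(2 × 0.0896 × 0.9104/124) = 0.0363; alternative SE 0.0358. Power ≈ Φ((0.0881 − 1.960 × 0.0363)/0.0358) = Φ(0.475) = 68%. Simulation gives 70%.
- Mean absolute deviation = 0.798 × SD: 1.596 v 1.197, difference 0.399 degrees. Its SD = 0.603 × SD: 1.206 v 0.904. SE = √((1.206² + 0.904²)/124) = 0.135. Power ≈ Φ(0.399/0.135 − 1.960) = Φ(0.99) = 84%. Simulation gives 84%.

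**Whole distribution narrows or moves (simulation, 20,000 runs; repeat runs agree within about 2 points).**

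| Assumed errors, manual v robotic | z-test on >3 degrees | Welch on absolute deviation | Gain, points |
|---|---|---|---|
| SD 3 v 2 | 94 to 95% | 99% | 4 to 5 |
| SD 2.5 v 2.0 | 51% | 62% | 11 |
| SD 2.5 v 1.9 | 69% | 80% | 11 |
| SD 2.0 v 1.5 | 70% | 84% | 14 |
| SD 1.8 v 1.4 | 54% | 74% | 20 |
| SD 1.5 v 1.2 | 32% | 63% | 31 |
| t with 5 df, SD 2.0 v 1.5 | 43% | 69% | 26 |
| Mean 1 v 0.3, SD 2 v 1.7 | 66% | 78% | 12 |
| Mean 1 v 0, SD 2 in both | 18% | 22% | 4 |

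Under the null both tests reject about 5% of the time. Stated as outlier rates under centred normal errors, the gain is about 2 points at 30% v 10% (98% v 99.8%), 14 at 15% v 5% (75% v 89%) and 35 at 5% v 1% (45% v 80%).

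**Only the share of gross misses differs (simulation, 10,000 runs).**

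| Assumed gross-miss component and its share | Other errors | z-test | Welch | Gain, points |
|---|---|---|---|---|
| SD 4 about the plan, 30% v 10% | SD 1.2 | 66% | 65% | −1 |
| SD 4 about the plan, 30% v 15% | SD 1.5 | 30% | 31% | +1 |
| Centred at 4 degrees, SD 0.7, 20% v 10% | SD 1.2 | 54% | 45% | −9 |
| Centred at 4 degrees, SD 0.7, 25% v 12% | SD 1.5 | 61% | 54% | −7 |
| Centred at 4 degrees, SD 0.7, 15% v 5% | SD 1.3 | 63% | 50 to 51% | −12 to −13 |

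A further set of mixtures (SD 1 with SD 4) gave −1 to +6 points.

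**The rotation test applied to limb alignment.** Mann-Whitney on absolute deviation stays close to the z-test in most centred normal cases (for example 49% v 52%, and 68% v 70%). In one gross-miss mixture, 10% v 2% outliers, it loses about 37 points. Copying the rotation analysis would therefore not secure the gain; comparing means is what produces it.

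**The case against.** The strongest case against the point has four parts.

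- **The planned test fits its hypothesis.** Hypothesis 4 is about outliers, and a test of proportions answers it. Mean absolute deviation is another estimand, and power for it is not power for hypothesis 4. This stands. A reader might infer that the z-test is wrong or should be replaced; the documents do not support that.
- **The gain is not a property of the plan.** A reader might infer that the plan throws away a fixed 4 to 30 points of power that a comparison of means would recover. With no outlier rate, SD or error shape in the documents, no such figure can be derived. Fewer outliers could equally mean fewer gross misses with unchanged routine accuracy, and there the added test ties or loses. This stands too.
- **The largest gains come where outliers are rare.** SD 1.5 v 1.2 means 4.5% v 1.2% outliers and a mean difference of only 0.798 × 0.3 = 0.24 degrees. The documents do not say what difference in degrees would matter. This is a reason to report the interval and not only a p-value.
- **The contrast with rotation proves little.** The rotation test is Mann-Whitney, which would add little here under centred normal errors. The contrast shows that absolute deviation is already an accepted variable. It does not show that the limb-alignment analysis is an error.

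It can also be said that nothing forbids descriptive reporting in degrees, and that the outcome is secondary. Both are true. But an analysis not fixed in advance would be post hoc, and the stated interest in accuracy has no planned comparison behind it for this outcome.

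**Conclusion.** The point holds as a cheap improvement. The plan measures limb alignment in degrees and names accuracy as a purpose, yet it tests only the proportion beyond 3 degrees.

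At 124 per arm, with normal or t5 errors and narrowing of the whole distribution, adding a comparison of mean absolute deviation typically brings about 4 to 30 points more power than the z-test. The gain approaches zero where the z-test is already near 100%, and reaches about 35 points at very low outlier rates. If only gross misses differ, the added test ranges from a small gain to a loss of about 13 points. Because the z-test is kept, a poor showing by the added analysis takes nothing from the test of hypothesis 4.

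The primary FJS comparison and the sample size are unaffected.

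**What to change.** Keep the 3-degree outlier percentage and its z-test as the stated test of hypothesis 4. Add one sentence to section F, radiographic outcome 1, before any comparison by group: as a supporting secondary analysis, mean absolute deviation in degrees from the planned mechanical limb alignment will be compared by Welch t-test, reported as a mean difference with 95% CI and read alongside the outlier percentage. The sentence should also say that a significant mean difference does not by itself establish fewer outliers.

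The cost is one sentence and one more analysis of measurements already planned, with no extra visit, image or patient. The downside is one more secondary test at 0.05, on a related but different estimand.
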